#### **14.1.3 Secondary Analyses of the ARR**

The secondary analysis of the primary endpoint (ARR at Month 24) will be conducted on the PP population using the same method as the primary analysis.

#### **14.1.4 Subgroup Analyses of ARR**

The subgroup analyses of the primary endpoint (at Month 24 for the ARR during the follow-up period) will be conducted on the FAS population.

A subgroup analysis at Month 24 of the ARR during the follow-up period for patients completing the study and patients who drop out will be performed. Estimates and CIs for the 2 subgroups will be reported using the same method as the primary analysis. This analysis will be repeated

considering the ARR based on all reported relapses, as described in the sensitivity analysis of the primary endpoint.

The same analysis will be performed for patients who complete treatment and for patients who do not complete treatment (i.e., completing Year 1 treatment but not Year 2 treatment) when the number of patients in the last group is greater than 10. This analysis will be repeated considering the ARR based on all the reported relapses, as described in the sensitivity analysis of the primary endpoint.

A subgroup analysis at Month 24 of the ARR during the follow-up period will be performed with reference to the type of MS at screening (RRMS, aSPMS, PPMS, and CIS). This analysis will be repeated considering the ARR based on all the reported relapses, as described in the sensitivity analysis of the primary endpoint.

For the primary outcome, the patterns of missingness will be explored. When the number of missing values is substantial (>5%), multiple imputation methodology will be considered for the analysis of the primary objective. At least 20 imputed datasets will be considered. The ARR at Month 24 for a patient will be considered missing if, for that patient, the number of relapses at Month 24 is missing or if the time on study for that patient is missing.

At least the following variables will be considered in the imputation model:

- ARR at Month 24
- Type of MS at screening
- Number of relapses in the previous 2 years
- Age
- Sex
- Baseline body mass index (BMI)
- Compliance

Since we have both continuous and categorical variables in the imputation model, the fully conditional specification method will be considered for the imputation. Predictive mean matching will be used for the imputation of the following variables: ARR at Month 24, number of relapses in the previous 2 years, age, baseline BMI, and compliance. The SAS code for the analysis is available in the appendices. This analysis will be repeated considering the ARR based on all the reported relapses, as described in the sensitivity analysis of the primary endpoint.

## 14.2 Other Efficacy Endpoints

Analysis (Analysis Population)	Derivation	Statistical Analysis Methods	Missing Data Handling
Secondary Endpoint: Relapses			
Secondary (FAS)	
A relapse will be defined as per routine clinical practice, as determined by the Investigator.
 
A relapse will be associated with hospitalization if the patient is hospitalized for the relapse.
	
The following statistics will be reported over the 12-month and 24-month periods:
 
 
• Proportion of patients experiencing a relapse
 
• Proportion of patients with relapse associated with hospitalization
 
• Proportion of patients with relapse associated with glucocorticoid use
 
• Proportion of patients experiencing no relapse
 
• Proportion of patients missing relapse data
 
	See description in Section 14
Secondary (PP)	
A relapse will be associated with glucocorticoid use if steroid treatment is required for the relapse.
		
Secondary endpoint: ARR at Month 12			
Secondary (FAS)	
ARR at Month 12.
 
The ARR of a patient is calculated as the number of relapses of the patient in the first 12 months divided by the number of days on study for that patient (maximum 1 year) and multiplied by 365.25. This variable will be considered to get population estimates.
	
The population estimate will be based on the average of the ARR values for the patients in the study. The SAS® MEANS procedure will be used to compute these quantities. The following descriptive statistics will be reported: mean, SD, min, max, median, first quartile (Q1), and third quartile (Q3).
	
Patients discontinuing early (before 12 months after the first dose of cladribine tablets) are analyzed according to the number of years of follow-up on treatment and the number of relapses observed up to the time of discontinuation.

Secondary (PP)	
A relapse will be defined as per routine clinical practice, as determined by the Investigator.
 
Time on study (days) = (min [(date of first dose of cladribine tablets + 365.25), (date of study discontinuation)] - date of first dose of cladribine tablets + 1)
		

Analysis (Analysis Population)	Derivation	Statistical Analysis Methods	Missing Data Handling
Secondary endpoint: Annualized relapsed rate (ARR) associated with hospitalization or glucocorticoid use			
Secondary (FAS)	
ARR associated with hospitalization or glucocorticoid use at Months 12 and 24.
 
The ARR associated with hospitalization (glucocorticoid use) of a patient is calculated as the number of relapses associated with hospitalization (glucocorticoid use) of the patient divided by the number of days on study for that patient and multiplied by 365.25. This variable will be considered to get population estimates.
 
A relapse will be defined as per routine clinical practice, as determined by the Investigator.
	
The population estimate will be based on the average of the ARR (associated with hospitalization or glucocorticoid use) values for the patients in the study. The SAS® MEANS procedure will be used to compute these quantities. The following descriptive statistics will be reported: mean, SD, min, max, median, first quartile (Q1), and third quartile (Q3).
	
Patients discontinuing early (before Month 12, or Month 24 on cladribine tablet treatment) are analyzed according to the number of years of follow-up on treatment and the number of relapses observed up to the time of discontinuation.

Secondary (PP)	
A relapse will be associated with hospitalization if the patient will be hospitalized for the relapse.
 
A relapse will be associated with glucocorticoid use if steroid treatment will be required for the relapse.
 
Time on study (days): Similar to previous definitions of time on study for primary and secondary ARR endpoints at timepoints of 24 months and 12 months, respectively, but taking into account the association with hospitalization or glucocorticoid use.
 
The above analyses will be repeated considering the ARR based on all the reported relapses, as described in the sensitivity analysis of the primary endpoint.
		
CCI			

15 Safety Analyses

Safety analyses will be done for the safety analysis population, i.e.:

- SAF for the first 24-month period.

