9.7.1 Analysis Sets

Full Analysis Set

The Full Analysis Set includes all patients enrolled in the study who received at least 1 dose of cladribine tablets.

Per Protocol Analysis Set

The Per Protocol Population includes all patients who have completed a full treatment course of cladribine tablets (2 weeks of treatment (4-5 doses per week) for years 1 and 2), according to the USPI and are compliant with all entry criteria.

Safety Analysis Set

The Safety Population includes all patients enrolled in the study who have received at least 1 dose of cladribine tablets (same as Full Analysis Set).

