### **6.4                    Third Interim Analysis**

The third interim analysis will be performed on the 12-month data for all patients.

This analysis will include all the endpoint analyses related to the objectives of the study. For the PROs, the actual value at each visit and the change in scores from Baseline to Months 6 and 12 will be considered. This analysis will allow interim assessment of all relevant aspects of the study.

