### Per-Protocol Analysis Set (PP)

The PP analysis set includes all patients who have completed a full treatment course of cladribine tablets (2 weeks of treatment [4-5 doses per week] for Years 1 and 2), according to the USPI, and are compliant with all entry criteria and without protocol deviations.

If the PP analysis population includes at least 90% of patients in the FAS analysis population, additional efficacy analyses on the Per-Protocol analysis population will be omitted, as differences in the results based upon these 2 analysis populations are expected to be negligible.

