### Additional Subgroup Analysis Populations

Analyses	Analysis Population		
	Full Analysis Set	Per-Protocol Analysis Set	Safety Analysis Set*
Baseline assessments (baseline characteristics of patients initiating cladribine tablets, baseline PRO data, baseline laboratory data, baseline data on previous MS DMD use, relapses during the previous 2 years [or since MS diagnosis if diagnosis <24 months], baseline MRI data, retrospective MRI data, and past treatment adherence)	✓	✓	✓
Compliance and exposure	✓		✓
Primary endpoint analysis (ARR over the 24-month period)	✓	✓	✓

Analyses	Analysis Population		
	Full Analysis Set	Per-Protocol Analysis Set	Safety Analysis Set*
Secondary endpoints analysis: The ARR over the 12-month follow-up period, Sensitivity analyses of the ARR, ARR during the last 24 months (or since MS diagnosis if diagnosis <24 months) before starting cladribine tablets, Other relapse analyses	✓	✓	✓
Treatment patterns (MS treatment during the last 2 years (or since MS diagnosis if diagnosis <24 months) before transition to cladribine tablets, concomitant treatment for MS, follow-up treatment in case of discontinuation of cladribine tablets)	✓		✓
PROs and treatment adherence	✓		✓
Analyses of MRI imaging data	✓		✓
CCl [REDACTED]	CCl [REDACTED]		■
Analyses of ALC, as well as complete blood count and lymphocyte subsets, if available	✓	✓	✓
Concomitant medications	✓		✓
Safety	✓		✓

AE: adverse event; ALC: absolute lymphocyte count; ARR: annualized relapse rate; DMD: disease-modifying drug; FAS: Full Analysis Set; CCl [REDACTED]; MRI: magnetic resonance imaging; MS: multiple sclerosis;

PRO: patient-reported outcome.

\*Remark: Safety Analysis Set coincides with FAS for this study.

Subgroup analyses will be performed for the primary endpoint on subgroups, as defined below.

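### The Month 12 per-protocol relapse rows use a set that requires completion of the Year 2 course, so membership depends on events after the 12-month outcome window and the results may be biased in either direction.

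*SAP*

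**What the plan says.** SAP 8.2 has one PP set. Patients must have "completed a full treatment course of cladribine tablets (2 weeks of treatment [4-5 doses per week] for Years 1 and 2", meet all entry criteria and have no protocol deviations. Protocol 9.7.1 has the same two-year requirement. Neither document defines a set based on Year 1 alone.

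SAP 14.2 gives this set a row for three groups of 12-month results:

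- relapse proportions: "The following statistics will be reported over the 12-month and 24-month periods"
- Month 12 ARR: "The ARR of a patient is calculated as the number of relapses of the patient in the first 12 months", divided by days on study (at most one year) and annualized
- "ARR associated with hospitalization or glucocorticoid use at Months 12 and 24"

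The population table in SAP 8.2 agrees. It ticks PP as well as FAS for the row beginning "Secondary endpoints analysis: The ARR over the 12-month follow-up period, Sensitivity analyses of the ARR".

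Two other provisions matter. SAP 8.2 omits the additional PP efficacy analyses if PP is at least 90% of FAS. SAP 6.4 says "The third interim analysis will be performed on the 12-month data for all patients" and includes all endpoint analyses.

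**The concern.** A 12-month outcome should be analysed in a set that can be determined by Month 12. Here a patient who took the Year 1 course correctly, met all criteria and was followed for the full year is removed from the Month 12 PP rows if the Year 2 course is later missed. If the reason for missing it is linked to first-year relapse, the set is selected on the outcome it is meant to describe. A PP value below the FAS value could then be read as a better result in adherent patients when selection alone produced it.

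The SAP shows the mismatch itself. The missing-data rule beside the Month 12 ARR rows is for patients who discontinue before 12 months. No such patient can belong to a set that requires the Year 2 course.

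**Working it through.** **Timing.** Protocol 9.2.2 places the treatment weeks at the start of the first and second months of each treatment year and allows Year 2 to be delayed by up to 6 months. The last Year 2 week therefore starts about 12 + 1 = 13 months after first dose, or 12 + 6 + 1 = 19 months with the full delay. Both are after Month 12.

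**Size.** The documents give no PP size, no expected Month 12 value and no completion rates by relapse status, so there is no plan figure to reproduce. All inputs below are assumptions.

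Let m be the first-year ARR, p the share with any first-year relapse, and c1 and c0 the probabilities of being in PP with and without a first-year relapse. For simplicity, every patient has a full first year of follow-up, and membership depends only on whether there was any relapse.

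- PP share of FAS: s = p × c1 + (1 − p) × c0
- PP ARR = m × c1 / s

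With m = 0.15 and Poisson counts, p = 1 − exp(−0.15) = 0.1393.

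| Non-completion, relapsers vs non-relapsers | s | PP ARR | Against 0.15 |
|---|---|---|---|
| 40% vs 10% | 0.1393 × 0.60 + 0.8607 × 0.90 = 0.858 | 0.0900 / 0.858 = 0.105 | 30% low |
| 25% vs 10% | 0.1393 × 0.75 + 0.8607 × 0.90 = 0.879 | 0.1125 / 0.879 = 0.128 | 15% low |
| 20% vs 15% | 0.1393 × 0.80 + 0.8607 × 0.85 = 0.843 | 0.1200 / 0.843 = 0.142 | 5% low |
| 15% vs 15% | 0.850 | 0.1275 / 0.850 = 0.150 | none |
| 5% vs 20% | 0.1393 × 0.95 + 0.8607 × 0.80 = 0.821 | 0.1425 / 0.821 = 0.174 | 16% high |

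In every row PP is below 90% of FAS, so the omission rule would not apply.

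The first case changes little under other inputs. With negative binomial counts and dispersion 1, p = 1 − 1/1.15 = 0.1304, and the PP ARR is 0.0900 / (0.1304 × 0.60 + 0.8696 × 0.90) = 0.105, again 30% low. With Poisson counts at ARR 0.25, p = 0.2212, and the PP ARR is 0.1500 / (0.2212 × 0.60 + 0.7788 × 0.90) = 0.180, which is 28% low.

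**Bounds for the relapse proportion.** For a given s, the PP proportion lies between max(0, (p − (1 − s))/s) and p/s. With an assumed FAS proportion of 0.20:

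- s = 0.899: (0.20 − 0.101)/0.899 = 0.110 to 0.20/0.899 = 0.223
- s = 0.80: 0.00 to 0.20/0.80 = 0.25

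These are extremes rather than expectations. They show that the 90% rule limits the distortion but leaves room for it.

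**The case against.** A reader might infer that the Month 12 PP rows understate first-year relapses. The documents do not support that as a fact. The reasons they give for withholding or stopping treatment are not relapse-based: lymphocyte non-recovery (Protocol 9.2.2), and pregnancy, HIV, active chronic infection and renal impairment (Protocol 11.4). The nearest support is a general remark in Protocol 7.3 that most disease-modifying drugs are continued unless ineffective or not tolerated. A downward bias is plausible, but it remains an assumption.

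A reader might also infer that nobody can qualify for PP at the third interim. That needs every patient's data to be cut at their own Month 12, which the SAP does not describe; SAP section 6 uses eCRF data up to a cutoff date. The last consent was on 28 November 2022, so the last patient reached Month 12 no earlier than 28 November 2023. Patients who started 19 months or more before that date, by about the end of April 2022, would have passed even a fully delayed Year 2 course. What stands is narrower: PP status is undetermined for patients who have not yet reached or finished Year 2 at the cutoff.

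The consequence is limited. Each affected row sits beside a FAS row, the primary analysis is on the FAS, and all tests are exploratory. Reasons for PP exclusion (SAP 10.2.2) and for stopping cladribine (SAP 13) are reported, and completers are compared with drop-outs (SAP 6.5). The rows may also be omitted under the 90% rule. All of this is correct and lowers the priority. It does not repair the rows if they are produced, because none of those tables corrects a Month 12 estimate for selection on Year 2 completion.

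Finally, SAP version 4.0 is dated 23 January 2025, after the planned last patient last visit of 3 January 2025, so the third interim is probably past. The final analysis still covers all endpoint analyses, including the Month 12 rows.

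**Conclusion.** The point holds as a defect in the choice of population. The only PP set requires completion of Year 2, it is assigned to 12-month outcomes, and no other section sets it aside for those rows. If PP is below 90% of FAS, the Month 12 PP results may be biased. Under the assumed ARR of 0.15 and the assumed completion rates, the result runs from about 30% too low, through no bias, to about 16% too high. The sign depends on whether first-year relapsers are less or more likely to complete Year 2, which the documents do not say. Even with no bias, the set drops patients who completed Year 1 as planned and is the wrong one for a 12-month per-protocol question. It should be changed, but no primary conclusion depends on it.

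**What to change.** For every Month 12 PP row in SAP 14.2, and for any 12-month interim still to be run or re-run, use a Year 1 PP set: Year 1 course completed according to the USPI, all entry criteria met, and the SAP 8.2 condition on protocol deviations applied through Month 12. Keep the two-course PP set for the Month 24 rows. Update the population table in SAP 8.2 and name the set in each table title. Alternatively, drop the Month 12 PP rows.

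The cost is a short SAP revision and one extra population flag, built from exposure and deviation data already collected. The Month 12 and Month 24 PP tables will have different N. Because the set would be added after the planned end of follow-up in a single-arm study, the change should be dated and explained in the SAP or, failing that, identified in the study report as unplanned, as SAP section 4 requires. Dropping the rows avoids adding a new population.

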## 15.1 Adverse Events

## Definitions

The recording period for AEs begins when the patient is initially included in the study (date of signature of first informed consent) and continues at least to the end of the mandatory safety follow-up period (i.e., up to 24 months in most patients or up to 30 months in patients with delayed start of Year 2 treatment).

TEAEs: Those AEs with onset dates occurring within the treatment period (i.e., after the first dose and until the end of the follow-up period).

For the analyses, ADRs will be those TEAEs reported in the eCRFs as related to study treatment or those AEs where such a relationship is missing.

All analyses described in Section 15.1 will be based on TEAEs unless otherwise specified.

Event rates (per patient-year of time on the study) will be calculated as the total number of events divided by the total time on study.

### **Missing Data Handling**

Incomplete AE-related dates will be handled as follows:

- In case the onset date is missing completely or missing partially, but the onset month and year, or the onset year, are equal to the start of the study dose, then the onset date will be replaced by the minimum of the start of the study dose and AE resolution date.
- In all other cases, the missing onset day or missing onset month will be replaced by 1.
- Incomplete stop dates will be replaced by the last day of the month (if only day is missing), if they do not result in a date later than the date of the patient's death. In the latter case, the date of death will be used to impute the incomplete stop date.
- In all other cases, the incomplete stop date will not be imputed. If the stop date of AE is after the date of cutoff, the outcome of AE is ongoing at cutoff.

### **15.1.1 All Adverse Events**

If an AE is reported for a given patient more than once during the study, the worst severity and the worst relationship to the study drug will be tabulated.

The following overall frequency table will be prepared:

- Any TEAEs
- Treatment-related TEAEs (ADRs)
- Any serious TEAEs
- Treatment-related serious TEAEs
- Any TEAE by severity (severe, moderate, mild)
- Treatment-related TEAE by severity (severe, moderate, mild)
- TEAEs leading to death
- Treatment-related TEAEs leading to death

The total number of TEAEs and the rate (per patient-year of time on study) of TEAEs will also be reported.

A table showing the TEAE by Primary SOC and PT will be reported.

A listing with the following columns will be presented:

- Patient ID
- AE
- PT term
- Start/end date of AE
- Duration of AE (days)
- Relationship to cladribine
- Action on cladribine
- Outcome
- Relative day from first administration
- SAE (Yes/No)

### **15.1.2 Adverse Events Leading to Study Treatment Discontinuation**

The following overall frequency table will be prepared:

- TEAEs causing temporary discontinuation of study treatment
- TEAEs causing permanent discontinuation of study treatment
- Any TEAEs leading to dose reduction of study treatment

For the above categories, the total number and rate (per patient-year of time on study) of TEAEs will also be reported.

## **15.2 Deaths, Other Serious Adverse Events, and Other Significant Adverse Events**

### **15.2.1 Deaths**

The following summaries for deaths will be reported in a table:

- Number and percentage of deaths
- Number and percentage for each reason of death (percentage calculated using the number of deaths as the denominator)

The total number of deaths and the rate (per patient-year of time on study) of deaths will also be reported.

A listing with the following columns will be presented:

- Patient ID
- Age (years)/sex/race/weight (kg)
- Date of first / last administration

- Last dose (unit)
- Number of doses
- Date of death
- Cause of death
- AE
- PT term

### **15.2.2                    Serious Adverse Events**

A listing with the following columns will be presented:

- Patient ID
- AE
- PT term
- Start/end date of AE
- Duration of AE (days)
- Seriousness criteria (results in death, is life-threatening, requires/prolongs hospitalization, persistent/significant disability/incapacity, is a congenital anomaly/birth defect, other)
- Relationship with study treatment (related, unrelated)
- Severity (severe, moderate, mild)
- Action(s) taken with study treatment
- Outcome of event (fatal, not recovered/not resolved, recovered/resolved with sequelae, recovered/resolved, unknown)
- Relative day from first administration

### **15.3                            Clinical Laboratory Evaluation**

Hematology assessment will be based on white blood cell count, hemoglobin, hematocrit, platelet count, and ALC. For continuous variables, values and changes from baseline values will be considered. The above variables will be evaluated descriptively by time point.

CCI

**CCI**

Any available results for immunoglobulin test will be summarized as a continuous variable with values and changes from baseline values by timepoint.

Laboratory values outside the normal range will also be flagged in the data listings, along with the corresponding normal ranges. The data listing will include the following columns:

- Patient ID
- Parameter (International System of Units [SI unit])
- Visit/week
- Date of collection (relative day)
- Value
- Change from baseline
- Lower range/upper range
- Normal range indicator (Low, high)

Boxplots of the laboratory values and boxplots of the change from baseline values will be reported by time point.

ALC will also be displayed as a line graph with the median cell counts on the Y-axis (with bars for 1st and 3rd quartiles extending above and below) and time points on the X-axis.

An additional summary of ALC by lymphopenia grade will be presented with the proportion of patients in each category at each time point:

- Elevated:  $>4.8 \times 10^9$  cells/L
- Normal:  $1.0$  to  $4.8 \times 10^9$  cells/L
- Grade 1 lymphopenia:  $0.8$  to  $< 1.0 \times 10^9$  cells/L
- Grade 2 lymphopenia:  $0.5$  to  $< 0.8 \times 10^9$  cells/L
- Grade 3 lymphopenia:  $0.2$  to  $< 0.5 \times 10^9$  cells/L
- Grade 4 lymphopenia:  $<0.2 \times 10^9$  cells/L

These categories are consistent with the Common Terminology Criteria for Adverse Event (CTCAE) for lymphopenia AE grading (US Department of Health and Human Services. CTCAE version 4.0. 2009;4(03)).

